Visit	Group	Parameter	Conjugated bilirubin	Creatinine level	Alkaline phosphatase
		N			
		Missed			
		Beyond the limit of detection			
		Mean			
		95% CI			
171	Treatment group:	SD			
V 1	$R-Maltofer^{\mathbb{R}}$	Median			
		Min			
		Max			
		Q1.25%			
		Q3.75%			
		IQR.75%			

STATISTICAL ANALYSIS PLAN

Visit	Group	Parameter	Conjugated bilirubin	Creatinine level	Alkaline phosphatase
		N			
		Missed			
		Beyond the limit of detection			
		Mean			
		95% CI			
	Treatment group:	SD			
	I – Ferrum Lek	Median			
		Min			
		Max			
		Q1.25%			
		Q3.75%			
		IQR.75%			
		Ν			
		Missed			
V5		Beyond the limit of detection			
	Treatment group:	Mean			
	R – Maltofer [®]	95% CI			
		SD			
		Median			
		Min			

SOP-05-02_RF01 Statistical Analysis Plan_01APR2020_3.0

STATISTICAL ANALYSIS PLAN

Visit	Group	Parameter	Conjugated bilirubin	Creatinine level	Alkaline phosphatase
		Max			
		Q1.25%			
		Q3.75%			
		IQR.75%			
		Ν			
		Missed			
		Beyond the limit of detection			
		Mean			
		95% CI			
	Treatment group:	SD			
	$T-Ferrum \; Lek^{\circledast}$	Median			
		Min			
		Max			
		Q1.25%			
		Q3.75%			
		IQR.75%			

Table 17. Biochemistry 3

Visit	Group	Parameter	Τ4	Vitamin B12	Creatinine index	TSH	Folic acid (B9)
V1 Treatment	Treatment group:	Ν					
V I	$R-Maltofer^{\ensuremath{\mathbb{R}}}$	Missed					

STATISTICAL ANALYSIS PLAN

Visit	Group	Parameter	Τ4	Vitamin B12	Creatinine index	TSH	Folic acid (B9)
		Beyond the limit of detection					
		Mean					
		95% CI					
		SD					
		Median					
		Min					
		Max					
		Q1.25%					
		Q3.75%					
		IQR.75%					
		Ν					
		Missed					
		Beyond the limit of detection					
		Mean					
	Treatment group:	95% CI					
	I – Ferrum Lek	SD					
		Median					
		Min					
		Max					
		Q1.25%					

SOP-05-02_RF01 Statistical Analysis Plan_01APR2020_3.0

STATISTICAL ANALYSIS PLAN

Visit	Group	Parameter	T4	Vitamin B12	Creatinine index	TSH	Folic acid (B9)
		Q3.75%					
		IQR.75%					

Table 18. Biochemistry, statistical test 1

Vi	sit	V1	V5	V1	V5	V1	V5	V1	V5	V1	V5
Vari	able	Al	LT	A	ST	Total j	Total protein		oilirubin	C-reactive protein	
Shapiro–	$\begin{array}{l} Treatment \ group: \\ R-Maltofer^{\circledast} \end{array}$										
Wilk test, p-value	Treatment group: T – Ferrum Lek [®]										
Student's t-t	æst, p-value										
Wilcoxon-Mann-W	/hitney test, p-value										

Table 19. Biochemistry, statistical test 2

Visit		V1	V5	V1	V5	V1	V5
Variable		Conjugated bilirubin		Creatinine level		Alkaline phosphatase	
Shapiro–	Shapiro– Treatment group: R – Maltofer [®]						
Wilk test, p-value	Treatment group: T – Ferrum Lek [®]						
Student's t-test, p-value							
Wilcoxon-Mann-W	/hitney test, p-value						

STATISTICAL ANALYSIS PLAN

Table 20. Biochemistry, statistical test 3

Visit		V1					
Variable		T4	Vitamin B12	Creatinine index	TSH	Folic acid (B9)	
Shapiro– Wilk test, p-value	$\begin{array}{l} Treatment \ group: \\ R-Maltofer^{\circledast} \end{array}$						
	Treatment group: T – Ferrum Lek [®]						
Student's t-test, p-value							
Wilcoxon–Mann–Whitney test, p-value							

STATISTICAL ANALYSIS PLAN

Adverse events	Group	Amount	% of the total number of AEs	% of the number of AEs by the medicinal product	p-value, Fisher's test
All adverse events	Т				
	R				
	Т				
SUC	R				
DT	Т				
F1	R				
DT	Т				
P1	R				
	Т				
	R				
SOC	Т				
	R				
РТ	Т				
	R				
РТ	Т				
	R				
	Т				
	R				

ADVERSE EVENTS Table 1. Adverse events reported in the study

STATISTICAL ANALYSIS PLAN

Tables N. Is the adverse event ongoing?/ Relatedness to the medicinal product/ Dose adjustment or temporary withdrawal of the IMP/ Complete withdrawal of the IMP/ Prescribing a concomitant medicinal product/ Prescribing non-drug therapy/ Patient admission to hospital or hospitalization prolongation/ Based on an AE/ Is it an SAE?/ Leads to death/ Threatens life/ Requires admission to hospitalization prolongation/ Leads to permanent or significant incapacity for work or disability

Adverse events	Group	{variable name]	Amount	% of the number of AEs by the medicinal product	p-value, Fisher's test
	Т	value			1
		value			
		value			
All adverse events		value			
	R	value			
		value			
	Т	value			- 1
		value			
SOC		value			
500	R	value			
		value			
		value			
РТ	Т	value			- 1
		value			
		value			
	R	value			
		value			
		value			

STATISTICAL ANALYSIS PLAN

Adverse events	Group	{variable name]	Amount	% of the number of AEs by the medicinal product	p-value, Fisher's test
DT	Т	value			
		value			
		value			1
Г1		value			
	R	value			
		value			
		value			
	Т	value			1
		value			
		value			
	R	value			
		value			
	Т	value			1
		value			
SOC		value			
30C	R	value			
		value			
		value			
РТ	Т	value			
		value			1
		value			I
	R	value			

STATISTICAL ANALYSIS PLAN

Adverse events	Group	{variable name]	Amount	% of the number of AEs by the medicinal product	p-value, Fisher's test
		value			
		value			
		value			1
	Т	value			
DT		value			
P1	R	value			
		value			
		value			
	Т	value			
		value			
		value			
	R	value			
		value			
		value

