#### 9.1.4 Safety parameteres analysis

Safety evaluation will include:

- 1) determination of the total number, incidence and severity of the folowing:
  - I. adverse events (AEs), regardless of their relationship to the treatment;
  - II. AEs associated or potentially associated with the drug;
  - III. AEs leading to discontinuation.

2) Gastrointestinal disorders (determined by means of a standardized MedDRA query for the corresponding symptoms), regarded by the Investigator as related to the study therapy, will be analyzed separately.

Methods of descriptive statistics will be used to represent the results. A comparison of the incidence of new AE cases in the study groups will be performed using the Fisher's exact test or

the chi-square test, depending on the number of proposed observations in one cell (<5 or  $\ge 5$ ), and a comparison of the severity (and the possible causality between the study drug and AE) will be conducted using the Cochran—Armitage test for linear trends for ordered categorical data.

3) Changes in the results of laboratory studies (conducted in the central laboratory) over time and the incidence of abnormal results of studies (based on the reference values of the central laboratory) will be summarized by group, and a comparison will be made between the groups using appropriate tests for quantitative and qualitative data (see below).

4) Changes in the vital signs over time and the incidence of pathological abnormalities revealed during physical examination will be summarized by group, and a comparison will be made between the groups using appropriate tests for quantitative and qualitative data (see below).

Comparison of quantitative data will be conducted using the t-test or the Mann—Whitney test, depending on the distribution normality (which will be estimated using the Shapiro—Wilk test).

Qualitative data will be compared using the exact Fisher's exact test or the chi-square test, depending on the number of proposed observations in one cell (<5 or  $\geq 5$ ).

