9.1. Adverse events

The safety assessment will include determining the total number, frequency, and severity of:

- 1. Adverse events (AEs), regardless of their relation to the treatment;
- 2. AEs associated or potentially associated with the medicinal product;
- 3. AEs requiring treatment discontinuation.

Adverse events will be coded using the MedDRA nomenclature in the latest version. These will be represented by the preferred term (PT) and systemic organ class (SOC).

Methods of descriptive statistics will be used to represent the results. Comparison of the incidence of new cases of AE in the study groups will be carried out using Fisher's exact test or Pearson's χ^2 test, depending on the number of observations in one cell (< 5 or \geq 5).

Changes in the results of laboratory tests over time and the incidence of abnormal test results (based on the reference values of the central laboratory) will be summarized by groups, and a comparison will be made between the groups using appropriate tests for quantitative and qualitative data.

Safety data will be analyzed using the methods designated for the application of efficacy data evaluation.

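### The SAP's adverse-event tables give percentages of AEs, not of patients, so the promised AE incidence by arm is not displayed and the unit of the Fisher test is left undefined

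*SAP*

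**What the plan says.** **The promise.** The SAP's text is "Comparison of the incidence of new cases of AE in the study groups will be carried out using" Fisher's exact or Pearson's chi-square test (SAP 9.1). Protocol 9.1.4 has the same commitment: "A comparison of the incidence of new AE cases in the study groups will be performed using" the same two tests. Protocol 4.1 repeats it. Protocol 9.1 adds a general rule that categorical data are reported as a count, a percentage and a 95% CI for the proportion. SAP 4.3.1 defines the safety population in subjects and analyses it by treatment actually received.

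**The shells (SAP Appendix 1, Adverse Events).** AE Table 1 has four data columns: *Amount*, the percentage "of the total number of AEs", the percentage "of the number of AEs by the medicinal product", and a Fisher p-value. The generic Tables N keep *Amount*, the second percentage and the p-value. Their subjects include "Is it an SAE?/ Leads to death/ Threatens life" and "Complete withdrawal of the IMP", as well as relatedness, hospitalisation and disability.

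**The unit of the test.** SAP 9.1 chooses between Fisher and chi-square "depending on the number of observations in one cell", without saying what an observation is. It then adds: "Safety data will be analyzed using the methods designated for the application of efficacy data evaluation".

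**The concern.** Incidence needs the patients at risk as its denominator. Both percentages in the AE shells use AEs instead, and no AE shell prints the number of patients in the arm. A reader of these tables could not tell what share of treated patients had any AE, a serious AE, or an AE that ended treatment. Safety is the trial's only secondary objective.

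The p-value adds to the difficulty. It stands next to percentages that describe how AEs divide among terms, not how likely a patient is to have one. *Amount* could mean events or patients. If events were the unit, repeat events in one patient would also be treated as independent.

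**Working it through.** No figure in the documents has to be reproduced. The check sets promise against layout, then asks whether the undefined unit could matter.

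**1. Promise against layout**

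| Item | Text of protocol and SAP | AE shells |
|---|---|---|
| Quantity | AE incidence by arm | share of AEs |
| Population | safety population, in subjects, as treated | no N printed |
| Display | count, %, 95% CI (protocol 9.1) | *Amount*, % of AEs, no CI |
| Unit of test | observations, unspecified | unspecified |

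The SAP uses a suitable format elsewhere. Its responder table (Secondary Endpoints, Table 1) gives, for each arm, the total observed, the number of responders, the percentage and a 95% CI.

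**2. A degenerate row.** In the all-AE row of AE Table 1, the by-product percentage is the arm's AEs divided by the arm's AEs. It is 100% in both arms whatever happens in the trial.

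**3. Could the unit change the result?** Assumed inputs:
- 168 patients per arm, the planned randomised number, used as the safety N.
- An index event at 23% on Maltofer, the rate the protocol gives for discoloured faeces (2.1.1 and 2.1.2): 0.23 × 168 = 38.6, taken as 39 patients with one such event each.
- 40 other AEs on Maltofer, range 20 to 60.

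All tests are two-sided Fisher exact, with Ferrum Lek given first.

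*(a) All AEs multiplied by the same factor on Ferrum Lek*

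| Factor | Share of AEs | p | Patients | p |
|---|---|---|---|---|
| 2 | 78/158 vs 39/79 (49% vs 49%) | 1.0 | 78/168 vs 39/168 (46% vs 23%) | 0.000012 |
| 1.5 | 58/118 vs 39/79 (49% vs 49%) | 1.0 | 58/168 vs 39/168 (35% vs 23%) | 0.030 |
| 1.25 | 49/99 vs 39/79 (49% vs 49%) | 1.0 | 49/168 vs 39/168 (29% vs 23%) | 0.26 |

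At factor 2, the share-of-AEs p-value stays at 1.0 with 20 or 60 other Maltofer AEs (78/118 vs 39/59; 78/198 vs 39/99).

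*(b) Index event equal in both arms, other AEs doubled on Ferrum Lek*

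| Other Maltofer AEs | Share of AEs | p | Patients | p |
|---|---|---|---|---|
| 20 | 39/79 vs 39/59 | 0.058 | 39/168 vs 39/168 | 1.0 |
| 40 | 39/119 vs 39/79 (33% vs 49%) | 0.026 | 39/168 vs 39/168 | 1.0 |
| 60 | 39/159 vs 39/99 | 0.013 | 39/168 vs 39/168 | 1.0 |

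A test on shares of AEs can therefore miss a true excess, as in (a), or report a difference where patient risk is equal, as in (b). The unit does not always matter: at factor 1.25 neither test is significant.

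**The case against.** A reader might infer that the SAP plans an event-level test, or that the promised comparison is absent altogether. The documents support neither.

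- The wording is incidence in the study groups, and the safety population is defined in subjects.
- The sentence sending safety data to the efficacy methods points to comparisons between independent samples of subjects.
- The shell provides a p-value cell for the all-AE row, where a test of the by-product percentage would be empty. That suggests the p-value was not meant to follow the adjacent column.
- *Amount* may mean patients. If it does and the test is run on patients, the Fisher column is the promised comparison and the conflicts in step 3 do not arise.

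The examples also rest on assumed counts. In (a) a common multiplier fixes the share of AEs by construction, and in (b) only the other AEs are inflated. They show sensitivity to the unit, not an expected result.

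All of this stands, and it limits the point to the display and the unstated unit. It does not remove it. Even with a patient-level test, the tables would print a p-value for one quantity beside percentages of another, with no N, no share of patients and no CI. Percentages of AEs are legitimate for describing event attributes such as ongoing status or treatment given, but not as the display of incidence.

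**Conclusion.** The AE shells are wrong as written, because their denominator does not match the incidence that the protocol and SAP promise. That follows from the column headings and needs no assumption. The unit of the Fisher test is undefined: the text leans towards patients without saying so. With the assumed counts in step 3, the choice of unit can move a p-value from 1.0 to 0.00001, or from 1.0 to 0.026 in the opposite direction. It cannot be concluded that an event-level test will be run.

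The consequence is limited to safety reporting. The primary non-inferiority conclusion is unaffected, and incidence can be recovered from the per-patient AE records. The correction should be made, preferably before results are seen: the trial is open-label, and fixing the unit in advance removes a later choice.

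**What to change.** 1. In AE Table 1, and in the Tables N for relatedness, complete withdrawal of the IMP, SAE, death, life-threatening events, hospitalisation and disability, add the number of patients with at least one event as n/N (%) with a 95% CI. N is the safety population by treatment actually received.
2. State in SAP 9.1 that the Fisher or chi-square test compares patients with at least one event against patients with none.
3. Replace *Amount* with separately labelled event counts and patient counts.
4. Keep percentages with an AE denominator as untested description only. This includes the Tables N on event attributes (ongoing, dose adjustment, concomitant drug or non-drug therapy).

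The cost is a change to the shells, one sentence in SAP 9.1 and minor reprogramming. AEs are already recorded per patient, so no new data are needed.
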